7.2.2 Sunitinib

Sunitinib: two 25 mg capsules PO QD, with or without food will be administered in 6-week treatment cycles: 4 weeks on/2 weeks off.

The time of day for administration of sunitinib should be consistent and the actual time the dose is taken should be recorded in the eDiary each day.

If the patient misses a dose of study medication, it should be taken as soon as it is remembered. A missed dose should not be taken, though, if it is close to the next dose. In this case, the next dose should be taken at the regular time. More than 1 dose of sunitinib should not be taken at a time.

If vomiting occurs after taking sunitinib, the patient should be instructed not to retake the dose. Patients should take the next scheduled dose of sunitinib. If vomiting persists, the patient should contact the investigator. Ondansetron or another serotonin-receptor antagonist may be used.

On clinic visit days the patient should be instructed to wait until he/she arrives at the study centre to take their study medication when instructed.

Patients should be advised to bring any unused sunitinib in the original blister packs, in addition to returning any empty blister packs to each clinic visit. Sunitinib dosing compliance

should be reviewed with the patient at each clinic visit, including the visit at the beginning of each cycle when study medication is dispensed.

7.3 Labelling

Labels will be prepared in accordance with Good Manufacturing Practice (GMP) and local regulatory guidelines. The labels will fulfil GMP Annex 13 requirements for labelling, where applicable for that country. Label text will be translated into local language.

7.4 Storage

All study medications should be kept in a secure place under appropriate storage conditions. The investigational product label on the pack specifies the appropriate storage.

7.5 Compliance

The administration of study medications should be recorded in the appropriate sections of the eCRF. Treatment compliance will be assessed by the tablet or capsule count and the information should be recorded in the appropriate section of the eCRF.

An eDiary will be provided to all patients. Patients will be asked to record the date and time of their self-administered doses in the eDiary on all study days in order to monitor compliance and aid in PK data interpretation for those taking savolitinib.

7.6 Accountability

The study medications provided for this study will be used only as directed in the Clinical Study Protocol. Details of treatment with investigational product for each patient will be recorded in the eCRF.

Patients must return all unused medication and medication containers to the clinic at the time of every visit for a pill count and reconciliation with the eDiary.

The study site staff at the investigational site will account for all drugs dispensed and returned and for appropriate destruction. Certificates of delivery, destruction and return must be signed.

7.7 Concomitant and other treatments

7.7.1 Permitted concomitant medications and treatments

Blood transfusions are allowed during the study.

Patients are permitted to receive granulocyte colony stimulating factor (G-CSF) or granulocyte-macrophage colony stimulating factor (GM-CSF) in accordance with the American Society of Clinical Oncology's (ASCO) guidelines

Patients may receive bisphosphonates and/or RANK ligand inhibitors like denosumab, or corticosteroids for the treatment of bone metastases. However, patients receiving sunitinib should avoid invasive dental procedures if they have ever received bisphosphonates. Any patient who has received bisphosphonates requires a maxillofacial exam prior to randomisation (see Table 1).

Limited field palliative radiotherapy may be used for the treatment of pain at the site of bony metastases that were present at baseline, provided the investigator does not feel that these are indicative of clinical disease progression during the study period.

7.7.2 Restrictions based on clinical pharmacology for both study medications

Refer to Appendix H for concomitant medications that should be restricted or used with caution.

Patients who have taken strong inducers or inhibitors of CYP3A4 or strong inhibitors of CYP1A2 within 2 weeks of randomisation are excluded from the trial. Herbal medications cannot be taken within 7 days of randomisation (3 weeks for St John's wort) or throughout the course of the study.

Savolitinib-specific restrictions based on clinical pharmacology

- Savolitinib is a weak inhibitor of OATP1B1, OATP1B3 and BCRP. Discontinuation of statins is advised unless considered essential, in which case, the patient should be prescribed the lowest available dose and monitored for the effects of increased statin exposure.
- Savolitinib and its major metabolite, M2, are weak competitive inhibitors of CYP2C8 (IC_{50} = [REDACTED] and [REDACTED] μ M, respectively). Those drugs defined as strong CYP2C8 substrates (almost exclusively metabolised by CYP2C8, such as Repaglinide and Rosiglitazone) should be used with caution.
- Savolitinib and its major metabolite, M2, are weak competitive inhibitors of CYP3A4/5 (IC_{50} = [REDACTED] and [REDACTED] μ M, respectively). Concomitant use of CYP3A4 substrates which have a narrow therapeutic range or CYP3A4 sensitive substrates during the trial should be avoided as far as possible unless considered essential by the investigator, in which case patients must be monitored closely for potentially increased toxicity due to drug-drug interactions.
- Savolitinib is not a substrate of P-glycoprotein (Pgp) but is a weak inhibitor in vitro (IC_{50} = [REDACTED] μ M). Drugs that are known to be affected by Pgp such as digoxin, quinidine, loperamide, saquinavir and ritonavir should be used with caution.
- Savolitinib is an inhibitor of MATE1 and MATE2K (IC_{50} [REDACTED]). Metformin should be used with caution and patients monitored for the effect of increased metformin exposure.

7.7.3 Other concomitant treatment

Other medication other than that described above, which is considered necessary for the patient's safety and wellbeing, may be given at the discretion of the investigator and recorded in the appropriate sections of the Case Report Form.

8. STATISTICAL ANALYSES BY ASTRAZENECA

8.1 Statistical considerations

A comprehensive Statistical Analysis Plan (SAP) will be prepared prior to the first subject randomised and any subsequent amendments will be documented, with final amendments completed prior to database lock. The aim of this study is to compare the efficacy and safety of savolitinib versus sunitinib. Analyses will be performed by AstraZeneca or its representatives. All personnel involved with the analysis of the study will remain blinded to aggregated results until database lock and protocol violators identified.

Due to termination of recruitment into SAVOIR, all secondary analyses will be descriptive.

Sample size estimate

Approximately 180 patients were planned to be randomised from 5 to 10 countries worldwide in approximately 50 to 75 sites. Recruitment to the study was closed on 22 November 2018. It is now estimated that approximately 50 patients will be randomised from 7 countries.

The initial assumption was that the true treatment effect had a hazard ratio (HR) of 0.6 (which would have translated to an approximate 3-month improvement in median PFS over an assumed 4-month median PFS for MET-driven patients on sunitinib, assuming PFS was exponentially distributed), 121 PFS events confirmed by BICR would have had to have been observed for the study to have 80% power to show a statistically significant difference in PFS at the two-sided 5% level. The smallest treatment difference that would have been statistically significant at the final analysis was a PFS HR of 0.69. Assuming 67% maturity; 180 patients would have been needed to be randomised. An interim futility analysis of PFS was planned to be conducted when a total of approximately 36 BICR-confirmed PFS events had been observed (30% of 121 PFS events, which was estimated to occur 17 months after the first patient had been randomised). Following IDMC endorsement to terminate recruitment into SAVOIR, the interim analysis will not occur.

[REDACTED]

[REDACTED]

[REDACTED]

Following IDMC endorsement to terminate recruitment into SAVOIR, a sample size-reassessment will no longer be performed.

8.2 Definitions of analysis sets

8.2.1 Full analysis set

The full analysis set (FAS) will include all randomised patients and will compare the treatment groups on the basis of randomised treatment, regardless of the treatment actually received. Patients who were randomised but did not subsequently go on to receive study treatment are included in the ITT population. Therefore, all efficacy and HRQoL data will be summarised and analysed using the FAS on an ITT basis.

8.2.2 Safety analysis set

The safety analysis set consists of all patients who received at least one dose of randomised treatment (regardless of whether that was the randomised therapy intended or indeed whether, in rare cases, they received therapy without being randomised), according to the treatment they actually received. PRO CTCAE data will be summarised using the SAS.

8.2.3 PK analysis set

All patients who receive at least 1 dose of savolitinib per the protocol, for whom any post-dose PK data are available and do not violate or deviate from the protocol in ways that would significantly affect the PK analyses will be included in the PK analysis set. The population will be defined by the Study Team Physician, Pharmacokineticist and Statistician prior to any analyses being performed. Where a protocol deviation impacts only part of a subject's data,

the affected portion of the subject's PK data will be excluded from PK analysis and summary statistics, and the remaining valid data will be utilised.

8.3 Outcome measures for analyses

8.3.1 Calculation or derivation of efficacy variables

8.3.1.1 Blinded Independent Central Review (BICR) of RECIST-based assessments

Review of radiological imaging data will be carried out using RECIST version 1.1. All imaging assessments including unscheduled visit scans will be collected on an ongoing basis and sent to the sponsor-designated vendor by the site following completion of each scan. All scans will be read by BICR after notification of Progressive Disease by the investigator. If PD is not centrally confirmed, each subsequent scan will be read by BICR once it is received and processed by the sponsor-designated vendor. Once the institution calls PD, the scans will be reviewed by two independent radiologists using RECIST 1.1 criteria and will be adjudicated if required. The radiologists will be blinded to treatment. Depending on the speed and completeness of image submission to the sponsor-designated vendor, the turn-around time should generally be within 10 days. All scans will be reviewed for the primary analysis even for the patients who do not have PD per local review.

For each patient, BICR will define the overall visit response data (CR, PR, SD, PD or NE) and the relevant scan dates for each time point (ie, for visits where response or progression is/is not identified). If a patient has had a tumour assessment which cannot be evaluated, then the patient will be assigned a visit response of not evaluable (NE).

8.3.1.2 Progression-Free Survival (PFS)

PFS is defined as the time from randomisation until the date of objective disease progression or death (by any cause in the absence of progression), regardless of whether the subject withdraws from randomised therapy or receives another anti-cancer therapy prior to progression. Patients who have not progressed or died at the time of analysis will be censored at the time of the latest date of assessment from their last evaluable RECIST assessment. However, if the patient progresses or dies after two or more missed visits, the patient will be censored at the time of the latest evaluable RECIST assessment prior to the two missed visits.

The PFS time will always be derived based on scan/assessment dates not visit dates.

RECIST assessments/scans contributing towards a particular visit may be performed on different dates. The following rules will be applied:

- Date of progression will be determined based on the earliest of the dates of the component that triggered the progression.
- When censoring a patient for PFS the patient will be censored at the latest of the dates contributing to a particular overall visit assessment.

The primary analysis of PFS will be based on BICR; PFS per investigator review will be a sensitivity analysis.

8.3.1.3 Objective Response Rate (ORR)

ORR rate is defined as the number (%) of patients with measurable disease with at least one visit response of CR or PR. Data obtained up until progression, or last evaluable assessment in the absence of progression, will be included in the assessment of ORR. However, any complete response or partial response, which occurred after a further anticancer therapy was received, will not be included in the numerator for the ORR calculation.

Summaries of ORR will be based on BICR; ORR per investigator review will be a sensitivity analysis.

8.3.1.4 Duration of Response (DoR)

Duration of response will be defined as the time from the date of first documented response on study medication until the date of BICR-confirmed progression or death in the absence of disease progression. The end of the duration of response should coincide with the date of progression or death from any cause used for the PFS endpoint. The time of the initial response will be defined as the latest of the dates contributing towards the first visit response of PR or CR. If a patient does not progress following a response, then their duration of response will use the PFS censoring time.

Summaries of DoR will be based on BICR; DoR per investigator review will be a sensitivity analysis.

8.3.1.5 Disease control rate (DCR)

Disease control rate at 6 months is defined as the percentage of patients who have a best objective response of CR or PR in that period or who have demonstrated SD for a minimum interval of 24 weeks (minus 1 week to allow for an early assessment within the assessment window, ie, 161 days) following the date of randomisation. Disease control rate at 12 months is defined as the percentage of patients who have a best objective response of CR or PR in that period or who have demonstrated SD for a minimum interval of 48 weeks (minus 1 week to allow for an early assessment within the assessment window, ie, 329 days) following the date of randomisation.

Summaries of DCR will be based on BICR; DCR per investigator review will be a sensitivity analysis.

8.3.1.6 Tumour shrinkage

Tumour shrinkage will be assessed using RECIST tumour response. The absolute change and percentage change from baseline in sum of tumour size at each assessment will be calculated.

The best change in tumour size will include all assessments prior to progression or start of subsequent anticancer therapy.

Summaries of tumour shrinkage will be based on BICR; tumour shrinkage per investigator review will be a sensitivity analysis.

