2.2 Secondary objectives

Secondary objective:	Outcome measure:
To compare the efficacy of savolitinib versus sunitinib in patients with MET-driven, unresectable and locally advanced, or metastatic papillary renal cell carcinoma (PRCC)	
 Overall Survival (OS) Objective Response Rate (ORR), duration of response (DoR) and best percentage change in tumour size by BICR using RECIST 1.1 criteria Disease Control Rate (DCR) at 6 and 12 months
To assess the impact of savolitinib and sunitinib on disease related symptoms and health-related QOL in this patient population	
 Mean change from baseline in FKSI-19 and FACIT-F scores
To evaluate the pharmacokinetics of savolitinib in this patient population	
 PK concentration data

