5.1 Efficacy assessments

5.1.1 Tumour assessments by CT or MRI scans (RECIST 1.1)

The baseline assessment will be performed no more than 28 days prior to the date of randomisation and as close as possible to the start of study treatment. Following the baseline assessment, subsequent tumour assessments should be performed every 6 weeks at the start of each cycle (± 7 days) during the first year and then every 12 weeks (± 1 week) thereafter up to the time of BICR-confirmed PD. Anonymised copies of all CT/MRI scans done for tumour evaluation will be sent to an AstraZeneca appointed Contract Research Organisation (CRO) for blinded independent central review as soon as possible following completion of each scan (see Section 5.1.2). All scans should be evaluated using RECIST assessments until BICR-confirmed progressive disease.

At baseline, the imaging modalities used for RECIST assessment will be contrast-enhanced CT (MRI where CT is contraindicated) scans of the chest, abdomen and pelvis with other regions as clinically indicated for the assessment of disease. The same imaging modality should be used for subsequent follow-up assessments and will cover chest (in those patients with disease in the chest or upper abdomen lymphadenopathy at baseline), abdomen and pelvis with any other regions imaged at baseline where disease was present. Any other sites where new disease is suspected should also be appropriately imaged.

Radiological examinations performed in the conduct of this study should be retained at the site as source data.

It is important to follow the assessment schedule as closely as possible. If scans are performed outside of the scheduled visit ± 7 -day window interval and the patient has not progressed, every attempt should be made to perform the subsequent scans at their scheduled time points. This schedule is to be followed in order to minimise any unintentional bias caused by some patients being assessed at a different frequency than others.

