8.4 Methods for statistical analyses

All efficacy analyses will be performed on the FAS populations. Results of all statistical analyses will be presented using a 95% confidence interval and 2-sided p-value.

The below mentioned general principles will be followed throughout the study:

- Descriptive statistics will be used for all variables, as appropriate. Continuous variables will be summarised by the number of observations, mean, standard deviation, median, minimum, and maximum. Categorical variables will be summarised by frequency counts and percentages for each category.
- Unless otherwise stated, percentages will be calculated out of the population total and for each treatment group.

Baseline will be the last assessment of the variable under consideration prior to the intake of the first dose of investigational product, except for efficacy variables. For efficacy variables, baseline is defined as the last visit prior to randomisation.

Efficacy and HRQoL data will be summarised based upon the FAS analysis set. Safety and treatment exposure data will be summarised based upon the safety analysis set by actual treatment received. Study population and demography data will be summarised based upon the FAS analysis set.

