8.4.2 Analysis of the secondary variable(s)

Objective Response and Disease Control Rates

ORR and DCR will be presented with a two-sided 95% CIs using Clopper-Pearson method (Clopper and Pearson, 1934). The number and percentage of patients in each response category (CR, PR, SD, PD, NE) will be summarised. Results may be summarised by the IMDC risk category if patient numbers permit.

Duration of response

Kaplan-Meier plots of duration of response in the responding patients will be produced.

Change in tumour size

The best change in target lesion tumour size from baseline (where best change in target lesions size is the maximum reduction from baseline or the minimum increase from baseline in the absence of a reduction) will also be summarised.

Waterfall plots (bar charts) indicating the best percentage change from baseline in sum of the diameters of TLs will be produced. Reference lines at the +20% and 30% change in tumour size levels will be added to the plots, which correspond with the definitions of progression and ‘complete or partial’ response respectively.

Overall Survival

Summaries (number of deaths, medians, and proportion alive at 1 year) and Kaplan Meier plots will be provided.

Time to second progression or death (PFS2)

Summaries (number of 2nd progression events or deaths, medians, and proportion alive at 1 year) and Kaplan Meier plots will be provided.

PRO analyses

Analyses on the FACIT-F, FKSI-19, EQ-5D-5L and PRO-CTCAE will be based on the instruments’ scoring manuals.

Descriptive statistics will be calculated for each scheduled visit/time point in the study, for each trial arm and as a total. These will report the number of patients, the number of EQ-5D questionnaires completed at each visit, the number and proportion responding to each dimension of the EQ-5D-5L. Additionally, summary statistics (eg, n, mean, median, sd, min, max) will be reported for the EQ-5D index score and the EQ-VAS score, and the change from baseline for the EQ-5D index score and the EQ-VAS score.

To support submissions to payers, additional analyses may be undertaken and these will be outlined in a separate Payer Analysis Plan.

Safety analyses

Safety data will not be analysed formally. Standard data summaries will be produced for safety data including (but not limited to):

- Summaries of AEs of any CTCAE grade – summarised by MedDRA preferred term and system organ class and CTCAE grade.
- Summaries of Grade 3 and above AEs.
- SAEs.

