Complete Response (CR)	Disappearance of all target lesions since baseline. Any pathological lymph nodes selected as target lesions must have a reduction in short axis to <10 mm.
Partial Response (PR)	At least a 30% decrease in the sum of the diameters of TL, taking as reference the baseline sum of diameters
Stable Disease (SD)	Neither sufficient shrinkage to qualify for PR nor sufficient increase to qualify for PD
Progressive Disease (PD)	At least a 20% increase in the sum of diameters of target lesions, taking as reference the smallest sum on study (this includes the baseline sum if that is the smallest on study). In addition to the relative increase of 20%, the sum must also demonstrate an absolute increase of at least 5mm.
Not Evaluable (NE)	Only relevant if any of the target lesions were not assessed or not evaluable or had a lesion intervention at this visit. Note: If the sum of diameters meets the progressive disease criteria, progressive disease overrides not evaluable as a target lesion response

F 4.3 Non-target lesions (NTL)

F 4.3.1 Evaluation of non-target lesions

All other lesions (or sites of disease) not recorded as TL should be identified as NTL at baseline. Measurements are not required for these lesions, but their status should be followed at subsequent visits. At each visit an overall assessment of the NTL response should be recorded by the Investigator. This section provides the definitions of the criteria used to determine and record overall response for NTL at the investigational site at each visit.

Table F3 Evaluation of non-target lesions

Complete Response (CR)	Disappearance of all non-target lesions since baseline. All lymph nodes must be non-pathological in size (<10 mm short axis).
Non-CR/Non PD	Persistence of one or more NTL
Progression (PD)	Unequivocal progression of existing non-target lesions. Unequivocal progression may be due to an important progression in one lesion only or in several lesions. In all cases the progression MUST be clinically significant for the physician to consider changing (or stopping) therapy.
Not Evaluable (NE)	Only relevant when one or, some of the non-target lesions were not assessed and, in the Investigator's opinion, they are not able to provide an evaluable overall non-target lesion assessment at this visit.

Note: For patients without target lesions at baseline, this is relevant if any of the non-target lesions were not assessed at this visit and the progression criteria have not been met.

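### Section 8.3.1.6 cuts off best change in tumour size before the progression scan, so patients progressing at their first scan get no value, in conflict with the waterfall plot in Section 8.4.2

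*Protocol*

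**What the plan says.** Section 2.2 lists "best percentage change in tumour size by BICR using RECIST 1.1 criteria" among the secondary outcome measures. Section 8.3.1.6 fixes which scans count: "The best change in tumour size will include all assessments prior to progression or start of subsequent anticancer therapy".

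Section 8.4.2 defines best change as "the maximum reduction from baseline or the minimum increase from baseline in the absence of a reduction" and specifies a waterfall plot: "Reference lines at the +20% and 30% change in tumour size levels will be added to the plots". It ties the +20% line to the definition of progression. Section 8.4 sets the population: "All efficacy analyses will be performed on the FAS populations". Under Section 8.2.1 that means all randomised patients.

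Three further provisions matter:

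- Section 8.3.1.2 dates progression by the scan component that triggered it.
- Section 5.1.1 sets the first follow-up scan at week 6, within 7 days either way: "subsequent tumour assessments should be performed every 6 weeks at the start of each cycle".
- Appendix F, Table F2 defines target-lesion progression as "At least a 20% increase in the sum of diameters of target lesions, taking as reference the smallest sum on study". Baseline counts as the smallest sum where it is the smallest, and growth of at least 5 mm is also required.

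**The concern.** Because progression is dated to the triggering scan, that scan is at progression and not before it. A patient who progresses at the week-6 scan, with no earlier unscheduled scan, therefore has no eligible post-baseline measurement. The protocol gives such a patient no value and no place in the plot, although the analysis is meant to cover all randomised patients.

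Missingness of this kind depends on the outcome. Patients lost through target-lesion progression are among the worst results on this endpoint, so the remaining summary looks better than it should. The loss falls more heavily on whichever arm has more early progression. With about 50 patients and secondary results shown only descriptively, the waterfall plot will be read directly, and several absent bars would change its appearance.

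**Working it through.** **1. The two sections side by side.** Take a patient with no reduction whose best change is +20% or more. Every eligible scan, including the first, is then at least 20% above baseline. At the first scan the smallest earlier sum is the baseline sum, so the 20% criterion of Table F2 is met there. The 5 mm criterion is met as well whenever 20% of the baseline sum is at least 5 mm, that is, whenever the baseline sum is at least 5 / 0.20 = 25 mm. That first scan is then progression, and Section 8.3.1.6 excludes it. Only a baseline sum below 25 mm with growth under 5 mm could give a bar at or above +20%: for example, 20 mm growing to 24 mm is +20% but only 4 mm. Section 8.3.1.6 thus nearly empties the region that Section 8.4.2 marks with a reference line.

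**2. Check of the planning assumptions (Section 8.1).** HR 0.6, two-sided 5%, 80% power, 1:1 allocation. Schoenfeld: events = 4 × (1.960 + 0.842)² / (ln 0.6)² = 31.4 / 0.261 = 120.3, rounded up to 121. This reproduces the stated 121. Also 121 / 180 = 67.2%, which agrees with the stated 67% maturity. The implied savolitinib median is 4 / 0.6 = 6.67 months.

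**3. Upper limit on patients without a value.** The protocol gives no figure for this endpoint. Under exponential PFS, the share with a PFS event by the first scan is 1 − 2^(−t / median). With t = 6 weeks = 42 / 30.44 = 1.38 months:

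- Sunitinib: 1 − 2^(−1.38 / 4) = 0.213; × 25 = 5.3 patients.
- Savolitinib: 1 − 2^(−1.38 / 6.67) = 0.134; × 25 = 3.3 patients.

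Over the scan window of 5 to 7 weeks the ranges are 18% to 24% and 11% to 15%. The 25 per arm is half of the approximately 50 patients now expected.

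**4. Other medians cited in the protocol.** Section 1.2.3 gives 8.1 months for sunitinib in the papillary subset of an earlier randomised trial. Section 1.1.3.3 gives 24.7 weeks for savolitinib in MET-driven Phase II patients.

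- Sunitinib: 1 − 2^(−1.38 / 8.1) = 0.111; × 25 = 2.8 patients.
- Savolitinib: 1 − 2^(−6 / 24.7) = 0.155; × 25 = 3.9 patients.

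The order of the arms reverses. These medians come from separate studies and are used here only to show that the direction is not fixed.

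**The case against.** The strongest reply is that the intended reading can be recovered. Section 8.4.2 counts increases and marks progression, Section 8.3.1.6 itself has change calculated at each assessment, and the ORR rule in Section 8.3.1.3 uses data up until progression. The phrase may therefore only mean that post-progression data are dropped. That is plausible, but the text that fixes the derivation still says otherwise. For ORR the difference is harmless, since a progression visit cannot be a response. Here it decides whether a patient appears at all. A programmer who follows Section 8.3.1.6 would drop the patient.

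A second reply is that such detail belongs in the SAP, which is not shown. An unstated rule could be left there. This rule is stated, and it conflicts with another section of the same protocol.

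Third, early progressors are not hidden: they are events in the PFS analysis, and Section 8.4.2 tabulates the PD and NE categories. This stands and limits the harm.

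A reader might also infer more than the protocol supports:

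- That the rule removes exactly the fastest-growing tumours. Progression can rest on new or non-target lesions alone, with target lesions stable or shrinking (Table F4), and the protocol gives no split.
- That 21% and 13% estimate the number of scans discarded. They count every PFS event by week 6, including deaths before any scan, who have no value under either rule.
- That the comparison is biased in a known direction or by a known amount. Step 4 of the check shows that the direction depends on the medians, and the protocol has no data on the size of change at first-scan progression.

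**Conclusion.** The point holds as an internal contradiction in a stated derivation rule. Read literally, Section 8.3.1.6 leaves first-scan progressors without a value and cannot be reconciled with the definition and the +20% line in Section 8.4.2. Under the original planning assumptions at most about 5 of 25 sunitinib and 3 of 25 savolitinib patients are affected; under the other cited medians, at most about 3 and 4. These limits rest on exponential PFS, a first scan at week 6 and equal arms of 25. The arm that loses more is whichever has more early progression.

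Section 8.1 makes all secondary analyses descriptive, so the consequence is a distorted summary and waterfall plot for a named secondary endpoint. No test of this endpoint is planned, and the primary PFS analysis is unaffected. The change is worth making because it is simple and the conflict is plain, but it is not a major threat to the trial.

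**What to change.** In Section 8.3.1.6, define best change over *all post-baseline assessments up to and including the assessment at which progression is recorded, and before the start of subsequent anticancer therapy*. This agrees with Section 8.4.2 and gives the +20% line a purpose. Patients who die or leave before any scan will still have no value.

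The cost is one phrase, carried into the SAP. The scans are already collected, and Section 8.3.1.1 already has them all read centrally for the primary analysis. Reported shrinkage will become slightly less favourable.
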